14.3 Justification of sample size

On the basis of 1600 LEMTRADA[®] patients, the fraction of patients with premature discontinuation of the RMP can be determined by a 95% confidence interval whose length does not exceed 5 percentage points. In subgroups containing at least 25% of the total random sample, this fraction can be determined by a 95% confidence interval whose length is less than 10 percentage points.

Undesirable events with an incidence of at least 0.00187 (1:534) will be observed with 95% certainty at least once in the random sample of 1600 LEMTRADA[®] patients.

14.4 Statistical evaluation

The statistical evaluation of all data recorded will be performed descriptively. On the basis of a previously established statistical analysis plan (SAP) drafted by the contract research institute Winicker Norimed GmbH and examined by Sanofi, the data will be evaluated and the results evaluated by tabular and graphical means. For the fraction of patients with premature discontinuation of the RMP, 95% confidence intervals were determined according to the method of Clopper and Pearson. The effect of subgroup membership on this discontinuation rate will be examined in logistical regressions.

In general, for continuous variables the number of patients, mean value, standard deviation, the number of patients, mean value, standard deviation, the five-number summary (minimum, lower quartile, median, upper quartile, maximum) and optionally additional suitable percentiles are determined for constant variables. For categorical variables, the absolute frequencies and percentage frequencies are indicated.

For mean values and estimated probabilities and, insofar as is reasonable for other parameters as well, 95% confidence intervals are determined. The evaluations will also be performed for subgroups defined in advance in the SAP. Depending on the number of subgroups established in the analysis plan, the confidence interval will be increased if necessary.

The evaluations of the questionnaires used, SDMT (attention), EQ-5D and PRIMUS (health-related quality of life), CGI-S (physician version)/ patient and WPAI questionnaires (assessment of ability to work) will be performed according to validated and published algorithms.

The statistical evaluations of the data are exploratory in nature.

Observation plan

On the basis of the tables and graphs, the Winicker Norimed GmbH contract research institute will prepare a final report and a summary of the results in English.

15. PUBLICATION

The results of this study will be published. This will take place in a well-respected, peerreviewed medical journal. The publication(s) will be prepared based on the final report. The physicians participating in this study will be informed about the results of the investigation by the corresponding publication(s).

The authors named in publications may include all persons who have made a substantial contribution to (1) design, data collection or analysis, interpretation of data; (2) preparation of the manuscript or substantial intellectual comments on the manuscript, and (3) finalisation and approval of the final manuscript.

16. ARCHIVING

All relevant documents of the non-interventional study will be archived for at least 10 years. The participating physician will only store the patient identification list and the patient consent declaration, likewise for at least 10 years.

17. ADVERSE EVENTS

17.1 General

LEMTRADA[®] is a product under special observation, and therefore during the observation period it is fundamentally necessary to record and document adverse events, regardless of whether a correlation with LEMTRADA[®] is seen. The following adverse events must be documented as individual instances on the (S)AE form:

- Any adverse event that has a fatal outcome, is life-threatening by nature, or leads to hospitalisation
- Any adverse event found on the list in the appendix

In addition, all suspected cases of adverse drug effects are to be documented as individual cases on the (S)AE form, thus all adverse events in which the physician or

Observation plan

the patient sees a link to LEMTRADA[®] or another medicinal product from Sanofi, Sanofi-Aventis, Winthrop, Zentiva or Genzyme.

In the patient questionnaires, an adverse event should always be considered and documented on the (S)AE form if a deterioration in the patient's condition was noted (e.g., hospitalisation)).

The data documentation can, for example, be done by an MS nurse. The medical evaluation/validation of whether an adverse event is actually involved is an obligation of the treating physician, who can best assess the individual patient and his/her medical history (e.g., laboratory values classified as adverse events depending on their clinical relevance). For each reported adverse event, the treating physician should provide an assessment of whether there is any indication of a link to the product. He is also responsible for sending the information to Sanofi via the IT system.

For each reported case, the doctor should provide an assessment as to whether there is any indication of a link to the product.

Because the frequency with which MS relapses occur is an efficacy criterion in this non-interventional study, the occurrence of MS relapses is only documented additionally as an adverse event on the AE/SAE form if the relapses occur outside the usual course of the disease.

If a side effect occurs that is related to a medicinal product other than the Sanofi, this must be reported as stipulated in the reporting obligations of the German Physicians' Professional Code of Practice to the Drug Commission of the German Medical Association (AKdÄ), the Federal Institute for Drugs and Medical Devices (BfArM) or the respective pharmaceutical company. This information is not reported additionally to Sanofi.

Adverse events (AE/SAE) verified by the treating physician which occur within the observation period of this NIS must be reported immediately (but at the latest within 24 hours) to the pharmacovigilance (drug safety) unit of Sanofi-Aventis Deutschland GmbH (see below), regardless of whether or not a causal link to the use of **LEMTRADA®** is suspected.

Observation plan

17.2 Definition of terms

An **adverse event (AE)** is defined as any adverse and unexpected event in research subjects or users in a study or examination, regardless of whether there is a link to the research product. This includes any disease or injury or unfavourable clinical symptoms (including clinically relevant changes in laboratory test values) occurring or worsening after taking or using the medicinal product, regardless of whether there is presumed to be a causal link to the .medicinal product. (Section 3 of the German GCP Ordinance [GCP-V])

The observation period for detecting **adverse events** is defined as the time period between the first use of **LEMTRADA®** and 48 months after the patient's last infusion cycle that was documented within the framework of this observational study.

A serious adverse event (SAE) regardless of the dose and manifestation,

- is any event with a fatal outcome or immediately life-threatening character (life-threatening means that the patient is in immediate danger of losing his or her life, but not that the patient might have died if the event were more severe).
- any event that—without planning and unpredictably requires hospital admission or prolongation of the hospital stay.
- any event that causes persistent incapacity, inability to work or substantial disruption of the patient's ability to conduct normal life functions (a significant disruption is present when the patient is substantially incapacitated by the event in his or her ability to manage normal activities of daily life).
- any event that corresponds to **congenital malformation** or another birth defect.
- events that require medical intervention to prevent **permanent injury**, a fatal outcome or **hospitalisation**.

Documentation of AE/SAE takes place in the LEMTRADA® module of the data sheet system MSDS^{3D}-TREAT-MS of MedicalSyn GmbH Stuttgart, which provides the database system on behalf of Carl Gustav Carus Management GmbH Dresden. The AE/SAE form is stored as both a paper-based form in the MSDS3D system and as an electronic Case Reporting Form (eCRF). AE/SAE reports recorded via the MSDS3D eCRF will be sent automatically by e-mail to the Sanofi-Aventis / Genzyme Pharmacovigilance Department. Hard copy documents must be FAXED to the

Observation plan

Pharmacovigilance Department at Sanofi-Aventis/Genzyme. The data are pseudonymised and can be traced back to the patient by the doctor upon enquiry from Pharmacovigilance via the contract number and patient identification list.

Adverse drug effects (UAW)

Adverse drug effects (side effects) of medications intended for use in humans are harmful and unintended reactions to the medication. This means that a causal link between the medication and the event at least cannot be ruled out. Adverse drug effects are basically independent of the appropriate use of the medicinal product. Therefore the definition of this term excludes consequences of, for example, overdosage, abuse, misuse, inappropriate use or administration errors.

Fig.: Pharmacovigilance process TREAT-MS

Observation plan

Adverse drug effects / adverse events / serious adverse events are to be documented on the "AE/SAE reporting form" and transmitted immediately (but at the latest within 24 hours after notification) by fax of e-mail to the following locations:

Pharmacovigilance

Sanofi-Aventis Deutschland GmbH [name] [contact] [contact]

Call centre: [name] (0.06 €/call (German landline); max. 0.42 €/min (wireless mobile))

Observation plan

19. ANNEX A: LIST OF ADVERSE EVENTS OF PARTICULAR MEDICAL SIGNIFICANCE

Pregnancy	
Symptomatic overdosage	
Malignant diseases	
Cervical dysplasia	
Other autoimmune diseases	
Infusion-related reactions	Symptom/Finding
	Anaphylactic reactions
Infections	Symptom/Finding
	Opportunistic infections
	Disseminated infections
Diseases of the blood	Symptom/Finding
	Leukocytopenia
	Agranulocytosis
Liver diseases	Agranulocytosis Anaemia Symptom/Finding
Liver diseases	Agranulocytosis Anaemia Symptom/Finding Transaminase elevation
Liver diseases	Agranulocytosis Anaemia Symptom/Finding Transaminase elevation
Liver diseases Nervous system disease	Agranulocytosis Anaemia Symptom/Finding Transaminase elevation Symptom/Finding
Liver diseases Nervous system disease	Agranulocytosis Anaemia Symptom/Finding Transaminase elevation Symptom/Finding ### PML
Liver diseases Nervous system disease Kidney disease	Agranulocytosis Anaemia Symptom/Finding Transaminase elevation Symptom/Finding ### PML Symptom/Finding
Liver diseases Nervous system disease Kidney disease	Agranulocytosis Anaemia Symptom/Finding Transaminase elevation Symptom/Finding ### PML Symptom/Finding Glomerulonephritis

###

special attention

16 APPENDIX 4

List of used variables in TREAT-MS

Note: List may not be exclusive, is at high level, and does not provide the operation definitions.

Variable in TREAT-MS, used in this PASS	Variable in TREAT-MS, used in this PASS Timing of measurement, used in this PASS PASS	
Visit date	Each visit	Data collection for each objective
Date of infusion performed with 100 mL At date of the first LEMTRADA infusion of a course		Defining exposed patients, index dates, and the LEMTRADA courses
Sociodemographic information		
Birth year Gender	Baseline	Patient characteristics
Objective 1a: indication	L	I
MS type (RRMS/ SPMS/ PPMS/ CIS/ undetermined)	Screening visit	MS type RRMS
Active RRMS (yes/no)	Baseline	Highly active disease
Number of relapses in the last 12 months and 24 months	Baseline	Relapses
Any prior MS treatment: therapy name with start and end date	Baseline	Prior DMTs
 MRI Was MRI performed? With contrast agent? Number of gadolinium-enhancing lesions 	At the screening visit and/or at the day of the first LEMTRADA infusion	MRI status
Objective 1b: contraindications		
Pre-existing diseases* by name with start date	Baseline	All contraindications
Is there hypersensitivity to the active substance or any of the other ingredients?	Baseline	Hypersensitivity

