7 RATIONALE AND BACKGROUND

7.1 BACKGROUND

LEMTRADA (alemtuzumab) is a recombinant humanised monoclonal antibody for the treatment of patients with relapsing-remitting multiple sclerosis (RRMS). LEMTRADA binds to CD52, a cell surface antigen present at high levels on T and B lymphocytes, and at lower levels on natural killer cells, monocytes, and macrophages. The LEMTRADA treatment plan consists of two LEMTRADA treatment courses administered one year apart, with up to two additional treatment courses if needed, administered at least 12 months after the prior treatment course. The first LEMTRADA treatment course consists of five LEMTRADA infusions delivered daily over five days. The following treatment courses consist of three LEMTRADA infusions delivered daily over three days. LEMTRADA has been demonstrated to be a highly efficacious agent in the treatment of RRMS with data from clinical trials demonstrating reduced relapse rates, reduced disability, reduced brain volume loss and improved Expanded Disability Status Scale (EDSS) scores.(2-4) However, LEMTRADA is associated with serious risks, including risk of cardiovascular events (temporally related to infusion), serious infections, and autoimmunemediated conditions.

In 2019, LEMTRADA was subject to a European Commission (EC) triggered procedure under Article 20 of Regulation (EC) No 726/2004 in which new and cumulative safety data were assessed by the European Medicines Agency (EMA) Pharmacovigilance Risk Assessment Committee (PRAC). The procedure concluded that LEMTRADA is associated with new and emerging safety events including both cardiovascular and additional autoimmune (AI) events. PRAC advised changes to the European Union (EU) summary of product characteristics (SmPC) indication, the list of contraindications and safety monitoring recommendations, to best ensure patient safety.

The newly restricted indication is as follows:

- Patients with highly active disease despite a full and adequate course of treatment with at least one disease modifying therapy (DMT) or
- Patients with rapidly evolving severe RRMS defined by two or more disabling relapses in one year, and with one or more Gadolinium enhancing lesions on brain magnetic resonance imaging (MRI) or a significant increase in T2 lesion load as compared to a previous recent MRI.

The newly revised list of contraindications is as follows:

- Hypersensitivity to alemtuzumab or any of the excipients;
- Human Immunodeficiency Virus (HIV);

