Germany	Patient charts	Yes Data on highly active disease status, previous treatments, and relapse history are collected in the TREAT-MS CRF. MRI data are collected for MRIs that possibly took place at the screening visit and/or at the day of first LEMTRADA infusion. Therefore, MRI data are not available in TREAT-MS for the entire baseline period (12 or 24 months) and is anticipated to unavailable for many patients.	 Hypersensitivity to alemtuzumab or excipients HIV Severe active infections until complete resolution Uncontrolled hypertension History of arterial dissection of the cervicocephalic arteries History of stroke History of angina pectoris or myocardial infarction Known coagulopathy, on anti- platelet or anti-coagulant therapy Other concomitant AI diseases (apart from MS) 	 There is a detailed CRF for the TREAT-MS study which is completed using data from hospital charts or other medical information available to treating physicians as per TREAT-MS protocol. The CRF collects information on two contraindications for LEMTRADA by targeted questions, including: Is there hypersensitivity to the active substance or any of the other ingredients? Is there an infection with HIV? Furthermore, pre-existing conditions, and test results (e.g., HIV test, test of various infections, serology) are
		months) and is anticipated to unavailable for many	Known coagulopathy, on anti- platelet or anti-coagulant therapy	
		patients.	Other concomitant AI diseases (apart from MS)	Furthermore, pre-existing conditions, and test results (e.g., HIV test, test of various infections, serology) are collected. Additionally, adverse event data collected between TREAT-MS enrolment and the initiation of a continuing course are used to indicate a contraindication for a subsequent course.

AI= Autoimmune; BP=blood pressure; CRF=case report form; CNK=National Code Number; ECG=electrocardiogram; FBC= full blood count; HR=heart rate; HIV=human immunodeficiency virus; MRI=Magnetic Resonance Imaging; MS=Multiple sclerosis; MSDS-3D=Multiple Sclerosis Documentation System-3D

Table 4: Feasibility of each data source in meeting objective 2a (monitoring prior to and during infusion) and objective 2b (long-term monitoring). Grey sections indicate not measurable.

	Type of data	Monitoring Prior to infusion	Monitoring during infusion	Long-term monitoring post- infusion	Notes	

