9.11 LIMITATIONS OF THE RESEARCH METHODS

The central limitation of this study is anticipated low numbers of exposed patients due to 1) the Article 20 procedure and subsequent EU SmPC change in January 2020 and 2) the Covid-19 global pandemic (please refer to Table 2 in 'Response to reviewers' document dated 30 November 2020). A feasibility analysis was submitted in 2022 to ascertain numbers of newly prescribed LEMTRADA courses in 2020 and 2021 (Section 9.9). Section 9.6 above provides the most recent patient counts in interim analysis 2023.

As highlighted in Table 3 and Table 4, each data source contributes in different ways to meeting the study objectives. For example, from medical chart data in the Czech Republic, UK, and Germany, data on cardiac monitoring, blood testing, and the indication and contraindication can be collected, although the data also have some limitations as detailed below. In the Belgian data source, data on ECGs and blood monitoring are not available. HR and BP are rolled into one variable called "cardio-monitoring". In Belgian data, a proxy definition will be used for the

indication which may lead to some misclassification (Appendix 1). Namely, the first part of the indication is measurable in Belgian data⁵, but the second part of the indication is not due to the lack of available data on MRI results⁶. Proxy definitions will also be required for contraindications in Belgian data. While validation studies do not exist for the exact proxies we propose in Belgian data; the method of using pharmacy data and hospital service data to detect cardiovascular, other chronic disease and other comorbidities is widely performed, demonstrates good validity and is a generally accepted method of detecting comorbidities.(23-26)

Some contraindications will not be measurable or may be only partially measurable. For example, HIV is not required to be reported by patients in the UK. Uncontrolled hypertension will not be measurable in Belgian data because blood pressure data are not available. Using proxies based on anti-hypertensive use would be inappropriate because it would not be known whether hypertension was controlled or not.

For TREAT-MS, we currently do not have information on the extent of missing data for laboratory tests. Crude, preliminary data indicate that approximately half of the patients in TREAT-MS do not have MRI data at baseline. Future analyses and reports will further evaluate the extent of missing data in the German data.

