3. QUERIES

The present prospective non-interventional study will collect data on unselected adult patients with active, relapsing-remitting multiple sclerosis who are being treated with LEMTRADA[®].

The goals of the studies are as follows:

- Determining and assessing the implementation of the LEMTRADA[®] Risk Management Plan (RMP) in routine clinical practice
- Fulfilment of the requirements arising from the RMP for early detection of suspected cases of newly occurring autoimmune diseases during LEMTRADA[®] treatment.
- Evaluation of the infusion phases and possible infusion reactions.
- Identifying and evaluating the patients with more than 2 treatment phases
- Benefits of treatment in subgroups of patients
- Determination of the EDSS over the period of observation
- Evaluation of patient satisfaction
- Description of patients' quality of life
- Description of cognition over the period of observation
- Description of ability to work over the period of observation
- Detection of exacerbations and their severity
- Compiling AE/SAE and AESI/SAESI
- General description of the use of LEMTRADA[®] under routine practice conditions

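### German objective 1a: Appendix 4 lets an active-RRMS flag stand for highly active disease, at odds with Table 3 and not stated as a limitation

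*Protocol*

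**What the plan says.** Section 7.1 gives part 1 of the restricted indication as "Patients with highly active disease despite a full and adequate course of treatment with at least one disease modifying therapy (DMT) or" part 2, which is rapidly evolving severe RRMS defined by relapses and an MRI criterion. Objective 1a (Section 9.8.1) is the proportion of first-ever users who meet either part.

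For Germany, three places bear on how part 1 is measured:

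- Table 3 (Section 9.3): "Data on highly active disease status, previous treatments, and relapse history are collected in the TREAT-MS CRF".
- Appendix 4, objective 1a: the field shown is "Active RRMS (yes/no", recorded at baseline, and its name and use in this study is "Highly active disease". Separate rows list relapse counts over 12 and 24 months, prior MS treatments with dates, and MRI with the number of gadolinium-enhancing lesions.
- Appendix 3, TREAT-MS observation plan, Section 3: the study collects data on "unselected adult patients with active, relapsing-remitting multiple sclerosis who are being treated with" LEMTRADA.

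Appendix 4 carries a caveat: "List may not be exclusive, is at high level, and does not provide the operation definitions". Section 9.3 adds that relapse severity is not collected in TREAT-MS, so relapse numbers are used for the indication. Section 9.11 reports from preliminary data that "approximately half of the patients in TREAT-MS do not have MRI data at baseline".

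**The concern.** Active disease is a weaker condition than highly active disease, and the label change turns on that difference. Objective 1a is restricted to new users so that every patient counted had to satisfy the narrower indication. A flag that records only active or not active fits the wider population TREAT-MS was set up to document. If it supplies the activity element, a previously treated patient with active but not highly active disease is counted as correctly indicated.

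The protocol does not prepare the reader for this. Table 2 says the German data allow the indication to be measured and attaches no proxy label. For Belgium, by contrast, the proxy is named and possible misclassification is acknowledged. The German weaknesses that are disclosed (relapse severity and MRI) are different ones. Results are reported by data source, so the German proportion stands as a primary result of its own.

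**Working it through.** No figure in the protocol depends on this mapping, so there is none to reproduce. The check is a comparison of texts, a direction argument and a size.

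**1. Texts side by side.** Section 7.1 requires highly active disease. Table 3 says that status is collected. Appendix 4 shows an active yes/no field and assigns it to highly active disease. Relapses, prior treatments and MRI have their own rows with their own stated uses, so the flag is the only listed field whose stated use is the activity status. Both texts are current: Section 5 records the German entry of Table 3 as updated, and Appendix 4 as added, in version 3.1.

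**2. Direction.** Let H be highly active, A active, D adequate prior treatment and P2 part 2 met. Assume every highly active patient is also active, so H is contained in A.

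- Intended numerator: (H and D) or P2.
- Numerator if the flag alone decides activity: (A and D) or P2.

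The second set contains the first, so this substitution can only raise the proportion. The excess is the number of patients who have D and A but neither H nor P2. It shrinks as other fields take over the decision.

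**3. Size.** Inputs are the objective 1a row of Table 5 (Section 9.6).

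- 27 + 63 + 16 + 8 = 114, which agrees with the stated total.
- German share: 8/114 = 7.0%. Without Belgium: 8/(63 + 16 + 8) = 8/87 = 9.2%.
- One patient in Germany: 1/8 = 12.5 percentage points.
- Upper limit on a crude all-source proportion, if all eight were wrong: 7.0 points (9.2 without Belgium).

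**4. Illustration.** Exact intervals are used, the method named under Table 6. The true count of 4 is an assumption, since the protocol gives no true rate.

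| German result | Proportion | Exact 95% CI |
|---|---|---|
| 8 of 8 counted as met | 100% | 63.1 to 100 |
| 4 of 8 truly met | 50% | 15.7 to 84.3 |

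Section 9.5.3 puts the last first visit in December 2020, so the eight should not grow materially.

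**The case against.** The strongest reply is that the decision rule is not in the protocol. Appendix 4 says it is high level and gives no operational definitions. The full feasibility analysis dealt with those, and the local operating protocols and the SAP may contain them. The text also points to more than the flag: Section 9.3 says relapse numbers are used for the indication, and Appendix 4 lists relapse counts, dated treatments and gadolinium lesions for the same objective. All of this stands.

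A reader might therefore go too far in four ways:

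- **That Germany cannot separate the restricted indication from plain active disease, or that part 1 reduces to any prior treatment.** This needs sole reliance on the flag, which is not shown. Dated prior treatments already separate an untreated active patient from part 1, and part 2 is partly assessable.
- **That nearly everyone is recorded as active.** This is plausible from the population documented, but no distribution of the flag is given. The observation plan sets no exclusion criteria, and the field allows a no.
- **That patients without MRI are scored as failing part 2.** The protocol does not say how they are scored. If they were, that error would pull the proportion down, so the net direction across both sources of error is not established.
- **That a floor for the German proportion can be computed from prior treatment.** The protocol gives no rate of prior treatment among these patients.

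What the reply does not remove is the mapping itself. The protocol fixes which field represents highly active disease, and Table 3 describes that content differently.

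**Conclusion.** The point holds in a limited form. Appendix 4 equates active with highly active disease, Table 3 says something else is collected, and no section lists this as a limitation. To the extent that the flag decides the activity element of part 1, the German proportion is biased toward compliance, by 12.5 points per misclassified patient. The effect on a crude all-source figure is at most 7.0 points, or 9.2 without Belgium.

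This rests on two assumptions: that highly active disease is a subset of active disease, and that the flag separates patients poorly in a cohort documented for active RRMS. How much weight the flag carries is not known from the protocol. With eight patients the German interval is wide under any definition, so the gain is in a valid and openly described measure rather than in precision. It is worth correcting because the objective is primary and the change is small.

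**What to change.** 1. Reconcile Table 3 with Appendix 4, so that both state what the TREAT-MS form records, and stop treating an active-RRMS yes as highly active disease.
2. Derive the German activity element from fields already listed: relapse counts over the last 12 and 24 months together with dated prior treatments, and gadolinium lesions where an MRI exists. Fix the cut-offs before the final analysis. The Belgian proxy should not be copied whole, because its second arm accepts one prior highly efficacious treatment without any evidence of activity.
3. Show the result based on the active-RRMS flag only as a sensitivity analysis.
4. Report patients who do not meet part 1 and have no MRI as not assessable, and give the proportion twice, counting them as met and as not met.
5. In Section 9.11, name the German measure as a proxy and state its likely direction of misclassification.

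The cost is a few lines of text and a recode of existing fields for eight patients. The German figure may fall, and activity visible only on MRI may be missed where no MRI is recorded. With so few patients, some cells may fall under the reporting limits of 3 or 5 described in Section 9.6, so the German source should confirm what can be shown.
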